Clinical data on the longevity of this type of restorations is scarce¹⁰. The aim of this study is to assess the short and long-term outcomes of endocrowns made from three different materials; Lithium disilicate ceramic (IPS e.max[®]), monolithic translucent zirconia and a hybrid ceramic (Vita Enamic[®]).

Material and methods:

Sample size calculation:

Sample size per each group was set at 20 restorations based on similar studies investigating the outcome of different restorations on root canal treated teeth.

Inclusion criteria:

Root canal treated molars with significant loss of tooth structure and supra-gingival margins that are scheduled for cuspal-covering indirect restorations are included in this study.

Exclusion criteria:

- Teeth with extensive cracks or fractures
- Teeth with deep subgingival margins
- Non-functional teeth (no opposing dentition)
- Teeth with advanced periodontitis

Following root canal treatment, teeth will be randomly allocated into one of three groups according to the material of the endocrown they will receive; group A (n= 20): IPS e.max lithium disilicate ceramic, group B (n= 20): monolithic translucent zirconia, and group C (n= 20): Vita Enamic hybrid ceramic. Preparation of all teeth will be performed by the same operator. Impressions will be made using a conventional 2-stage putty and wash silicone impression material (**We'll choose one**) and the same dental technician will provide all the endocrowns by milling them from CAD/CAM blocks. Cementation will be done under rubber dam isolation using the recommended protocol for each material.

Clinical follow-up assessment will be made at 6 months, 1 year, 2 years and 5 years post-operatively. This will include assessment of the restoration integrity, marginal integrity and marginal discoloration, pink and white aesthetic scores and pocket probing depths.

Radiographic assessment will be made at 1 year, 2 years and 5 years post-operatively to detect the presence of restoration defects and recurrent caries.

Patient satisfaction will be assessed on a visual analogue scale (0-10)

All assessments will be done by an experienced independent clinician unaware of the material used.

Statistical analysis

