Non-parametric tests will be used to discern any statistically significant difference between groups. Wilcoxon signed-rank and Mann-Whitney tests will be used for tooth integrity, marginal integrity and discoloration, PES&WES and patient's satisfaction. Non-parametric T-test will be used for radiographic parameters.

Weibull distribution will be used to predict long-term survival rates per each group.

Funding:

This research needs funding to cover the cost of a) the lab fees of fabricating 60 endocrowns and b) the resin cement systems. Please see attached sheet.

Data collection form (appendix 1):

Patient: _____
DOB: _____
Tooth: _____
Material (coded): _____
Date: _____

ID: _____
Phone no.: _____
e-mail: _____

a- Clinical examination:

Endocrown failure: Yes / No (Specify type of failure) _____

Weeks from cementation to failure: _____

Modified USPHS criteria (use Alpha, Bravo, Charlie and Delta as in the key)

Margins: _____

Anatomic form: _____

Texture: _____

Colour match: _____

BoP/ pockets: _____

b- radiographic examination:

Secondary caries (0: absent, 1: present) _____

Proximal caries in adjacent teeth (0: absent, 1: enamel, 2: dentine) _____

Excess cement (0: absent, 1: detectable, 2: gross): _____

Periapical infection: (0: absent, 1: present/ improving, 2: present/ not improving or getting worse) _____

c- Patient-reported satisfaction (use the VAS below):

Shade: _____

Shape: _____

Quality of proximal contacts
(Food impaction/ ability to floss) _____

Chewing ability _____

Overall satisfaction _____

1	2	3	4	5
 Very dissatisfied	 Dissatisfied	 Neutral	 Satisfied	 Very satisfied

References:

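### Three independent arms, but only a paired test and a two-group test are named for the clinical scores and satisfaction, with no overall test or multiplicity rule

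*Combined protocol and SAP*

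**What the plan says.** Under Material and methods, "teeth will be randomly allocated into one of three groups", with 20 teeth per material. No pairing or matching of teeth across groups is described. On timing: "Clinical follow-up assessment will be made at 6 months, 1 year, 2 years and 5 years post-operatively".

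The Statistical analysis section states its purpose as follows: "Non-parametric tests will be used to discern any statistically significant difference between groups". It then gives three lines of method:

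- Clinical scores: "Wilcoxon signed-rank and Mann-Whitney tests will be used for tooth integrity, marginal integrity and discoloration, PES&WES". The same sentence goes on to include patient satisfaction.
- Radiographs: "Non-parametric T-test will be used for radiographic parameters".
- Survival: "Weibull distribution will be used to predict long-term survival rates per each group".

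The data collection form (appendix 1) grades several clinical items on a four-level scale, "Modified USPHS criteria (use Alpha, Bravo, Charlie and Delta as in the key", and has a field for "Weeks from cementation to failure".

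The document gives no significance level, sidedness, list of pairs to compare, visits at which tests are run, overall three-group test, multiplicity rule or primary outcome.

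**The concern.** The question is whether three materials differ, and neither named test answers it in one step. Signed-rank needs paired values. It suits change within an arm between visits, but it does not compare materials. Mann-Whitney compares two independent arms, so the three-material question becomes A-B, A-C and B-C, each with its own chance of a false positive.

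The other two lines do not fill the gap. The radiographic test is not a defined three-group procedure. The Weibull model predicts survival within each group and does not compare groups.

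Each single Mann-Whitney p-value is valid. What is unprotected is the conclusion that one material differs from another, because any one of three tests can produce it. With the pairs unstated, the choice of comparison could also be made after the data are seen. For survival, no between-material test is named, although the time to failure is recorded.

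**Working it through.** **Inputs from the document.** Three randomised groups, 20 teeth each, four clinical visits, and the tests quoted above. The plan states no error rate, so there is no figure of its own to reproduce.

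**Assumptions.** Two-sided 5% per test, all three pairs tested, independent teeth, no true difference, and a range of score distributions.

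**Reference values for three tests at 5%.**

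- Bonferroni bound: 3 × 0.05 = 15%.
- If the tests were independent: 1 − 0.95³ = 14.3%.
- Both overstate the risk, because the pairs share arms. With equal arms and large samples, at least one pair is significant when the range of three independent standard normal values exceeds 1.96 × √2 = 2.77. That probability is 12.2%.

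**Simulation at 20 per arm.** Tie-corrected Mann-Whitney with continuity correction, 20,000 null trials per row. The gate is a Kruskal-Wallis test at 5%, by chi-square for the continuous score and by permutation for the others. The two five-level gate figures use 4,000 trials (standard error about 0.35 percentage points). Graded scores are shown as the percentage in each grade.

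| Score distribution | Any of 3 pairs | Any of 2 pairs | Gate, then pairs |
|---|---|---|---|
| Continuous | 12.1% | 8.9% | 4.8% |
| Five levels, equal | 12.0% | 8.8% | 5.3% |
| Five levels, skewed | 11.7% | 8.6% | 4.8% |
| 60/30/10 | 11.7% | 8.6% | 4.8% |
| 70/25/5 | 11.8% | 8.8% | 4.8% |
| 85/12/3 | 11.4% | 8.4% | 3.7% |
| 90/8/2 | 10.0% | 7.2% | 2.9% |
| 95/4/1 | 2.9% | 2.2% | 0.9% |
| 95/5 | 2.7% | 2.0% | 0.8% |
| 97/3 | 0.8% | 0.6% | 0.3% |

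A separate run of 60,000 trials gave 12.1% for a continuous score and 11.3-12.0% for a four-level score split 70/20/8/2. With 16 per arm (an assumed 20% loss) the range was 11.1-12.2% across well-spread scores. For a continuous score, changing the per-test level to 1% or 10% moves the three-pair risk to 2.3% or 21.7%.

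**Why the gate suffices for three groups.** If all three materials are equal, a false positive first needs a false overall result, which has a 5% chance. If exactly one pair is equal, only that pair can give a false positive, and it is tested at 5%. No other null case exists with three groups. In simulation with A = B and C shifted by 0.5/0.8/1.0 SD, the false A-B rate was 4.0/4.7/4.9%.

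**Limit of the gate.** It works within one outcome and visit. For one continuous outcome tested at all four visits (assumed), the chance of any false positive is 34.8/30.1/22.3% ungated and 15.5/14.0/9.4% gated, at between-visit correlations of 0.5/0.7/0.9.

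**Log-rank power at 20 per arm.** Exponential failure times assumed. Expected failures are 20 × the sum of the three risks, for example 20 × (0.10 + 0.10 + 0.30) = 10.

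| 5-year failure by arm | Expected failures | Power, no dropout | Power, 20% lost by 5 years |
|---|---|---|---|
| 5/5/15% | 5 | 16% | 15% |
| 10/10/20% | 8 | 14% | 12% |
| 10/10/30% | 10 | 39% | 36% |
| 10/10/40% | 12 | 67% | 63% |

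With no true difference and a common 5-year failure risk of 10/20/30%, the gated log-rank procedure gave a false positive in 2.6/4.4/4.7% of trials.

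**The case against.** The strongest reply is that 11-12% describes an assumed procedure. The plan states neither the 5% level nor that all three pairs are tested, and four-level clinical grades may cluster so heavily at the top that there is no inflation. That stands as a limit on the size. It does not remove the gap: 85/12/3 still gives 11.4% and 90/8/2 gives 10.0%. Satisfaction and the aesthetic scores may be better spread, and testing only two pairs still gives 8.4-8.9% for distributions from continuous to 85/12/3.

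Second, signed-rank may well be meant for change between visits. With four visits that is the ordinary reading, so the fault is an unstated purpose. It leaves Mann-Whitney alone to compare three materials.

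Third, the general opening sentence of the analysis section could be read to cover survival. Even so, no survival comparison is named, and the log-rank test proposed below has low power in most scenarios. Failures found only at a visit would also be known only to an interval, and the last interval runs from 2 to 5 years. These points limit what the comparison can show. They do not make it better to have none.

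Fourth, Kruskal-Wallis is not the only remedy. Bonferroni or Holm applied to the Mann-Whitney tests already named gives 3.9% on a continuous score. That is a valid alternative with less power: 18/50/74% for Holm against 24/60/82% with the gate, for one arm shifted by 0.5/0.8/1.0 SD.

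**Conclusion.** The concern holds. For the clinical scores and satisfaction, the plan names no test that compares three independent arms together and no rule for several pairwise tests. Under the stated assumptions, the false-positive risk per outcome and visit is about 11-12% for well-spread and moderately clustered scores, more than double 5%. It is about 10% at 90/8/2 and below 5% once roughly 95% of teeth share a grade. Independence of teeth is assumed, because the document does not say whether a patient may contribute more than one.

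This should be fixed but is not fatal. No single p-value is wrong and the data to be collected are adequate for the repair. The absence of a named survival comparison matters as well, because survival is the outcome in the title.

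**What to change.** Settle the following wording before outcome data are seen:

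1. Compare the three materials on each score with a Kruskal-Wallis test, using a permutation p-value because of ties. Run pairwise Mann-Whitney tests at 5% only if the overall p is below 0.05. Holm over the three pairs is acceptable if preferred. State the level and sidedness.
2. Restrict signed-rank to change within an arm between named visits.
3. Compare time to failure with a three-group log-rank test (permutation p-value if failures are few), followed by pairwise log-rank at 5% only if the overall test is significant. Define failure, and record the interval when the date is not known. Keep the Weibull model as description.
4. Replace the radiographic line with a named three-group test suited to each item: an exact or permutation test for present/absent items, Kruskal-Wallis for the graded ones.
5. Name one primary outcome and visit. State that the gate does not control error across outcomes and visits, and label all other results exploratory.

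No extra teeth, visits or measurements are needed. The cost is pairwise power. On a continuous score with one arm shifted by 0.5/0.8/1.0 SD, it falls from 32/67/85% to 24/60/82%. On a graded score (85/12/3 against 60/30/10), it falls from 42% to 36%. The plan should also say that 20 per arm gives low log-rank power when failures are few, and that a non-significant result must not be read as equal survival.

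### The test named for the radiographic outcomes cannot be identified, and no three-group test or multiplicity rule accompanies it

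*Combined protocol and SAP*

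**What the plan says.** The Statistical analysis section gives one sentence to the radiographic outcomes: "Non-parametric T-test will be used for radiographic parameters". It does not define the test. The sentence before it assigns Wilcoxon signed-rank and Mann-Whitney tests to the other clinical and patient-reported outcomes, so something different seems to be intended here.

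The radiographic part of the Data collection form (appendix 1) has four coded items:

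- "Secondary caries (0: absent, 1: present"), which is binary;
- "Proximal caries in adjacent teeth (0: absent, 1: enamel, 2: dentine"), three levels;
- "Excess cement (0: absent, 1: detectable, 2: gross"), three levels;
- "Periapical infection: (0: absent, 1: present/ improving, 2: present/ not improving or getting worse"), three levels.

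Under Material and methods, "teeth will be randomly allocated into one of three groups according to the material of the endocrown they will receive". Each group has 20 restorations, and radiographs are taken at 1, 2 and 5 years. The plan states no significance level, sidedness, overall three-group test, scheme of pairwise comparisons or multiplicity rule, and no expected event rate.

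**The concern.** A t-test is ordinarily a parametric method, so the phrase leaves the analyst to decide what is meant. It could be an ordinary t-test, a rank test such as Mann-Whitney, or a permutation test on the t statistic. With 20 teeth per group and coarse codes, these can fall on opposite sides of 0.05 for the same data. If the choice is made after the data are seen, it can decide the result. Recurrent caries is one of the two stated purposes of the radiographs, so a named outcome is affected.

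The second difficulty is the number of groups. A two-sample test has to be run three times to compare three materials. With no overall test and no adjustment, the chance of at least one false positive among the three pairs can exceed the level of each test.

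**Working it through.** **Inputs.** From the documents: three groups, n = 20 per group, one 0/1 code, three 0/1/2 codes, three radiographic visits. Assumed, because the documents are silent: two-sided 5% per test, three unadjusted pairwise tests, no dropout, and a common true event rate from 2% to 50%. The plan states no p-value or error rate for these outcomes, so there is no figure of its own to reproduce.

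**Step 1. One data set, three readings (secondary caries, 4/20 v 0/20).**

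- Pooled t-test. Difference in means 4/20 − 0 = 0.20. Within-group sum of squares 4(0.8²) + 16(0.2²) = 3.2. Pooled variance 3.2/38 = 0.0842. Standard error √(0.0842 × 2/20) = 0.0918. t = 0.20/0.0918 = 2.18 on 38 df, p = 0.036.
- Mann-Whitney, normal approximation with tie correction and no continuity correction. U departs from its null mean by 20 × 20 × 0.20/2 = 40. Variance (400/12) × [41 − (36³ − 36 + 4³ − 4)/(40 × 39)] = 33.33 × 11.08 = 369.2. z = 40/19.2 = 2.08, p = 0.037 (0.040 with continuity correction).
- Fisher's exact test, which on 0/1 data gives the same p-value as an exact permutation t-test. 2 × C(20,4)/C(40,4) = 2 × 4845/91390 = 0.106.

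The same split occurs at 6/20 v 1/20: t 0.038, Fisher 0.091.

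**Step 2. Chance of any false positive among three pairs, one 0/1 code at one visit.** Let all three groups have true rate p. For counts a, b, c from 0 to 20, sum Bin(a; 20, p) × Bin(b; 20, p) × Bin(c; 20, p) over every triple in which at least one pairwise p-value is 0.05 or less. This covers all 21³ outcomes exactly.

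| True event rate | Any of 3 pairs: t or uncorrected Mann-Whitney | Any of 3 pairs: exact (Fisher / permutation t) | One pair: t |
|---|---|---|---|
| 2% | 0.2% | 0.01% | 0.1% |
| 5% | 2.8% | 0.5% | 1.2% |
| 10% | 9.8% | 3.2% | 3.9% |
| 15% | 12.0% | 5.3% | 4.9% |
| 20% | 11.9% | 5.8% | 5.0% |
| 30% | 12.9% | 6.3% | 5.3% |
| 40% | 11.6% | 6.1% | 4.8% |
| 50% | 10.2% | 5.1% | 4.3% |

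The t-test and the uncorrected Mann-Whitney test agree to the digits shown. A single pair never goes much above 5%, so the excess comes from having three pairs and no adjustment.

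**Step 3. The 0/1/2 codes** (simulation, 4,000 runs; standard error near 10% is √(0.1 × 0.9/4000) = 0.5 percentage points). Any-pair error with unadjusted Mann-Whitney (continuity-corrected) / t: 2.7% / 2.7% when 95% of teeth score 0, 10.1% / 10.2% when 90% do, 10.6% / 11.1% when 80% do, and 11.8% / 12.6% with equal categories. The pattern matches Step 2.

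**Step 4. One overall test instead.** Fisher-Freeman-Halton on the 0/1 code, by exact enumeration: 0.1% at an event rate of 2%, 0.9% at 5%, 2.3% at 10%, 3.8% at 30%, 4.4% at 50%. Ordinary (large-sample) Kruskal-Wallis on the 0/1/2 codes, simulated: 3.3% to 4.8%. Both stay within 5%.

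**The case against.** Three points can fairly be made for the plan.

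First, a reader might infer that the named test does not exist and cannot be run. The documents do not support that. Permutation t-tests exist, and the section opens by committing to non-parametric tests, which makes an ordinary t-test the reading least supported by the text. The defect is that the test is undefined, not that it is impossible. This does not rescue the sentence, because a permutation t-test and a Mann-Whitney test are both non-parametric and disagree in Step 1 (0.106 v 0.037).

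Second, a reader might infer that the plan roughly doubles its error rate. As a general statement that is unsupported. It holds only for three unadjusted pairwise t or large-sample rank tests at event rates of about 10% or more. Where findings are rare the error is below nominal, and under an exact reading it peaks at about 6.3% at the rates checked. The documents give no event rate, significance level or pairwise scheme that would settle which case applies.

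Third, the gap in Step 1 is one between large-sample and exact p-values. It would remain if the sentence had said Mann-Whitney without specifying the exact form. The missing three-group test likewise affects the outcomes assigned to Mann-Whitney in the preceding sentence. Both observations are right. They mean that the replacement wording must specify exact tests, and that the multiplicity gap is not peculiar to the radiographic sentence and should not be counted as a separate fault for each outcome.

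**Conclusion.** The point stands in limited form. The sentence does not identify a test, a t-type test does not by itself compare three groups, and plausible readings can give opposite conclusions from the same 20-per-group data. That much follows from the documents and from direct calculation, and it is firm.

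The error rate is conditional. Under two-sided 5% and three unadjusted pairwise t or uncorrected Mann-Whitney tests, the chance of any false positive for secondary caries at one visit is about 10-13% at true event rates of 10-50%. It falls to 2.8% at 5% and 0.2% at 2%. These assumptions are the reviewer's, not the plan's.

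This should be corrected, but it does not invalidate the trial. It concerns analysis wording and can be settled without any change to the data collected.

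**What to change.** Replace the sentence on radiographic parameters with wording that does the following:

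- Secondary caries: Fisher-Freeman-Halton exact test across the three groups at two-sided 5%. Only if it is significant, pairwise Fisher exact tests. Report risk differences with 95% confidence intervals.
- The three 0/1/2 codes: exact (permutation) Kruskal-Wallis test at two-sided 5%. Only if it is significant, pairwise exact permutation rank tests.

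With three groups this order holds the family at 5% for each code at each visit. If all three materials are equal, the overall test is the guard. If only two are equal, only one true pairwise null remains, and its own exact test limits the error. The follow-up tests must be exact for this to be guaranteed, since a large-sample pairwise test can reach about 5.3%.

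The protection does not extend across the 4 codes × 3 visits = 12 overall tests. As an illustration, 12 independent tests at a full 5% would give 1 − 0.95¹² = 46%; the true figure would differ, because repeated visits are correlated and exact tests run below 5%. The report should say that error across codes and visits is not controlled.

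The cost is a few lines of analysis text. The downside is that exact tests are somewhat conservative when events are few, as the Fisher-Freeman-Halton rates of 0.1% and 0.9% at event rates of 2% and 5% show.

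### Endocrown failure and its timing are recorded, but the plan assigns them no between-material test, difference or interval, only a per-group Weibull prediction with no stated horizon

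*Combined protocol and SAP*

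**What the plan says.** The title makes survival of endocrowns by ceramic the topic. The aim, at the end of the background, is broader (short- and long-term outcomes of three materials), and no primary endpoint is named. Teeth are randomised to three groups of 20.

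- **Visits** (Material and methods): "Clinical follow-up assessment will be made at 6 months, 1 year, 2 years and 5 years post-operatively". On content: "This will include assessment of the restoration integrity", followed by margins, aesthetic scores and probing depths.
- **Data collected** (Data collection form, appendix 1): "Endocrown failure: Yes / No (Specify type of failure") and "Weeks from cementation to failure".
- **Comparisons** (Statistical analysis): a general opening, "Non-parametric tests will be used to discern any statistically significant difference between groups", then specific assignments. "Wilcoxon signed-rank and Mann-Whitney tests will be used for tooth integrity, marginal integrity and discoloration", together with the aesthetic scores and satisfaction; radiographic parameters get a separate test.
- **Survival** (Statistical analysis): "Weibull distribution will be used to predict long-term survival rates per each group". Nothing further is said on survival.

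**The concern.** Failure and time to failure are on the form but not on the list of outcomes that receive a test. The survival sentence yields one predicted rate per material. It gives no difference, interval, censoring rule or time point, and does not say whether three separate fits or one model with material as a factor is meant.

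Followed as written, a randomised comparison of materials would have no planned comparison of failure that allows for censoring. Three predicted percentages without intervals invite ranking by eye, and with 20 teeth per arm chance alone can separate them widely.

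**Working it through.** **1. What is assigned to failure.** The plan has no figure here to reproduce; the check is of the text. Named tests cover tooth integrity, margins and discoloration, aesthetic scores, satisfaction and radiographs. Failure and weeks to failure are absent. The form has no line called integrity; the nearest are the failure item and "Anatomic form". A rank test of integrity is therefore at most a partial proxy, and it ignores both when a tooth failed and teeth lost to follow-up.

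**2. Arms with no failures.** Input from the plan: n = 20 per arm. Assumed, because the plan gives no rate: 5-year failure risk p of 5, 10, 15 or 20%, all teeth followed.

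- P(no failure in an arm) = (1 − p)^20 = 0.358 / 0.122 / 0.039 / 0.012.
- P(at least one of three arms has none) = 1 − (1 − that value)^3 = 0.74 / 0.32 / 0.11 / 0.03.

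With no events the Weibull likelihood has no finite maximum for that arm's scale. A shape shared across arms does not cure this.

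**3. Chance gaps between identical materials.** Simulation with 10,000 trials per risk: Weibull shape 1, exact failure times, no dropout, separate maximum-likelihood fits. Only trials with at least one failure in every arm can be fitted: 1 − 0.322 = 68% of trials at 10% risk and 1 − 0.034 = 97% at 20%. Share of those trials in which the highest and lowest predicted survival differ by 20 points or more:

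| Horizon | 10% risk | 20% risk |
|---|---|---|
| 5 years | about 6% | about 26% |
| 7 years | about 45% | about 53% |
| 10 years | about 73% | about 76% |

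An extreme illustration of the mechanism: take 20 teeth, one failure and the rest intact at 5 years. The fit is S(h) = exp(−h^k / Σt_i^k). A failure at year 1 gives shape k = 0.63, S(5) = 0.95 and S(10) = 0.92. A failure at year 4.5 gives k = 9.7, S(5) = 0.95 and S(10) of about 0.

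**4. Same measure for Kaplan-Meier at 5 years.** With complete follow-up, Kaplan-Meier survival is 1 − failures/20, so a 20-point gap means that the largest and smallest failure counts differ by at least 4. Summing the exact binomial probabilities gives 8.9% / 32.5% in the same fittable trials and 14.5% / 34.3% in all trials, against about 6% / 26% for Weibull. Gaps at 5 years come from n = 20, not from the Weibull model.

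**5. Precision of a proper contrast.** For 3/20 v 1/20 failures the difference is 0.15 − 0.05 = 0.10. Clopper-Pearson limits are 0.032 to 0.379 and 0.001 to 0.249. Combining them by square-and-add:

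- lower limit: 0.10 − √[(0.15 − 0.032)² + (0.249 − 0.05)²] = −0.13;
- upper limit: 0.10 + √[(0.379 − 0.15)² + (0.05 − 0.001)²] = +0.33.

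For 0/20 the upper limit for failure is 17%. Three-group permutation log-rank power at a 5% level, for assumed 5-year failure risks: 14% (5/5/15%), 22% (5/10/20%), 39% (10/10/30%), 65% (5/5/30%).

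**6. Censoring at the last visit.** There is no visit between years 2 and 5. Assume a constant hazard, so S(2) = S(5)^0.4, and let c = 1 − S(5)/S(2). At 10% risk S(2) = 0.9587 and c = 0.0613; at 20% risk, 0.9146 and 0.1253.

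- *Intact teeth miss year 5 (share q), every failure is reported:* the estimate is S(2)[1 − c/(c + (1 − c)(1 − q))]. For q = 0.10 at 10% risk: 0.9587 × (1 − 0.0613/0.9061) = 0.894, or 0.6 points too low. For q = 0.30 the shortfall is 2.3 points at 10% risk and 4.1 at 20%.
- *10% of intact and 30% of failed teeth are lost, unreported:* S(2)[1 − 0.7c/(0.7c + 0.9(1 − c))] is 1.2 points too high at 10% risk and 2.3 at 20%. Counting missing teeth as intact to year 5 gives S(2)(1 − 0.7c), 1.8 and 3.4 points too high.

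The bias can run either way, and in the second case both rules err upward.

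**The case against.** The best defence is that the opening sentence promises non-parametric tests between groups without limiting the outcomes, and a log-rank test is one. Integrity, which overlaps with failure, is rank-tested. The title is a noun phrase, the aim speaks of outcomes, and no survival hypothesis is stated. This stands to the extent that it would be wrong to say failure can never be compared under the plan. It does not supply a comparison: no failure test is named, and none of the tests listed is described as handling censored times.

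A second defence is that long-term may simply mean 5 years, the last visit. That is a natural reading, and the 7- and 10-year figures are then hypothetical. The missing contrast and interval remain on either reading.

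Third, with 20 teeth per arm a test would seldom be significant. That is true, and it argues for estimates with intervals rather than for no comparison.

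**Conclusion.** The point holds as an omission that should be fixed. No test, difference or interval is assigned to failure or time to failure, and the sole survival analysis has no contrast, interval or horizon. That rests on the text alone. The sizes rest on assumed failure risks and, for the gap figures, on Weibull shape 1, complete follow-up and the exclusion of trials with a failure-free arm.

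A reader might infer more than the documents support:

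- *That the Weibull model creates false differences at 5 years.* It does not; Kaplan-Meier shows gaps of 20 points at least as often.
- *That the plan extrapolates beyond follow-up.* It states no horizon. The instability is large only if it does.
- *That separate fits are the cause, so that one common-shape model is the cure.* The plan does not say which is meant, and neither gives a finite estimate for an arm with no failures.
- *That two alternative censoring rules would bracket the true survival.* They need not if failed teeth are preferentially lost.

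**What to change.** Replace the Weibull sentence with wording such as:

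> Time to first recorded endocrown failure is measured from cementation; other teeth are censored at the last assessment. Kaplan-Meier survival per material is reported at 1, 2 and 5 years with 95% confidence intervals from a method that stays defined when no tooth fails, together with the between-material differences at 5 years with 95% confidence intervals and one three-group log-rank test (permutation version, because events are few). A sensitivity analysis assigns failures to the visit interval in which they occurred. Any Weibull prediction states its horizon, is shown with intervals, and is labelled exploratory beyond 5 years; for an arm with no failures only a lower limit is given.

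**Cost.** Analysis wording only; the form already holds the data. The plan should state these limits:

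- Power is low and intervals are wide, so the emphasis is on estimation. A non-significant test is not evidence of equivalence.
- The intervals treat teeth as independent, although the plan does not limit teeth per patient.
- Last-visit censoring understates survival if only failures are reported and overstates it if failed teeth are preferentially lost. No claim should be made that other censoring rules bracket the truth.
- Prediction beyond 5 years becomes exploratory.

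### With 20 teeth per arm followed for at most 5 years, the per-group Weibull prediction may have no estimate or hang on one failure date; observed 5-year survival should be the main survival result

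*Combined protocol and SAP*

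**What the plan says.** The Statistical analysis section gives one sentence on survival: "Weibull distribution will be used to predict long-term survival rates per each group". No Kaplan-Meier estimate, confidence interval, prediction horizon, shared parameter or fallback is mentioned.

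The data available to that analysis are set elsewhere in the document:

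- Size: "Sample size per each group was set at 20 restorations", justified only as "based on similar studies investigating the outcome of different restorations on root canal treated teeth". No failure rate or expected number of failures is stated.
- Follow-up: "Clinical follow-up assessment will be made at 6 months, 1 year, 2 years and 5 years post-operatively". Nothing is scheduled after that.
- Event: the data collection form (appendix 1) records failure as yes or no with its type, and the weeks from cementation to failure.

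The aim, at the end of the background, reads: "The aim of this study is to assess the short and long-term outcomes of endocrowns made from three different materials". The time meant by long-term is not defined.

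**The concern.** A two-parameter Weibull needs failures. The scale is estimated from how many there are, and the shape from when they occur. Beyond the last visit the prediction is driven by the shape. With 20 teeth in an arm, the number of failures by 5 years may well be none, one or two unless failure is common.

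Two consequences follow. An arm with no failures gives no fit, so the better a material does, the less likely it is to get a prediction at all. An arm with one or two failures gives a number, but one set almost entirely by the dates of those failures. The study is titled as a survival study and this is its only survival analysis. The plan also does not say what to do if an arm cannot be fitted, so that choice would be made after seeing the data.

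**Working it through.** **Inputs.** From the documents: 20 teeth per arm, three arms, follow-up to 5 years, failure time recorded in weeks. Assumed, because the documents give no value: 5-year failure probability p, a 10-year prediction horizon, and true Weibull shape 1.5 or 1.0. The group size of 20 cannot be reproduced, because no error rate, power, effect or event rate is stated.

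**Step 1. How often an arm has no failure or at most one.** Per arm, P(0) = (1 − p)^20 and P(0 or 1) = (1 − p)^20 + 20p(1 − p)^19. For at least one of three independent arms with equal rates, P = 1 − (1 − P(0))^3.

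| Assumed p | P(0), one arm | P(0 or 1), one arm | P(some arm has 0) |
|---|---|---|---|
| 5% | 0.358 | 0.736 | 0.736 |
| 10% | 0.122 | 0.392 | 0.322 |
| 20% | 0.012 | 0.069 | 0.034 |

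**Step 2. No failures.** The log-likelihood is −Σ(t/scale)^shape. It rises towards 0 as the scale goes to infinity, so there is no finite estimate. The limit is 100% survival at every horizon, which predicts nothing.

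**Step 3. One failure at time t, with 19 teeth censored at 5 years.** Solving the likelihood equations gives shape k = 1.019 / ln(5/t). Fitted 5-year survival is exp(−1/19.361) = 0.95 whatever t is. Predicted 10-year survival is 0.9497^(2^k).

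| Date of the one failure | Shape | Predicted 10-year survival | 95% profile interval |
|---|---|---|---|
| 1 year | 0.63 | 0.92 | 0.53 to 0.99 |
| 2 years | 1.11 | 0.89 | 0.11 to 0.99 |
| 3 years | 1.99 | 0.81 | about 0 to 0.99 |
| 4 years | 4.57 | 0.29 | about 0 to 0.98 |
| 4.5 years | 9.67 | about 0 | about 0 to 0.97 |

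The observed result is the same in every row: 19 of 20 survive. Only one tooth's date changes.

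**Step 4. Spread over repeated trials.** 3,000 simulated trials of 3 × 20 teeth, identical materials, full follow-up, exact failure dates and maximum-likelihood fits. Arms with no fit are excluded. True 10-year survival is (1 − p)^(2^shape); for example 0.9^(2^1.5) = 0.9^2.83 = 0.74.

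| Shape | p | True 10-year survival | Separate fits, 5th to 95th percentile |
|---|---|---|---|
| 1.5 | 10% | 0.74 | 0.00 to 0.91 |
| 1.5 | 20% | 0.53 | 0.00 to 0.82 |
| 1.0 | 10% | 0.81 | 0.00 to 0.93 |
| 1.0 | 20% | 0.64 | 0.12 to 0.86 |

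**Step 5. Common shape, arm-specific scale.** At p = 10% the range narrows to about 0.2 to 0.90 (shape 1.5) or 0.46 to 0.92 (shape 1.0). An arm with no failures still has no finite scale, so its P(0) in step 1 is unchanged.

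**Step 6. What an observed 5-year result gives.** With 0 failures in 20 teeth all followed to 5 years, the two-sided 95% Clopper-Pearson upper limit for failure is 1 − 0.025^(1/20) = 0.168, about 17%. This is usable in exactly the case where the Weibull fit fails.

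**The case against.** - **The failure rate is unknown, and failures may not be rare.** This stands. Failure is not defined tightly, and a broad definition would give more events. At 20% failure an arm has at most one failure with probability only 7%. More failures remove the no-fit problem, but step 4 shows that the imprecision beyond 5 years remains at 20%.
- **Separate fits are not stated.** This stands in part. One model with material as a covariate would also give a rate per group. Separate fits are the natural reading, and a single model would still not fit an arm with no failures.
- **The 10-year horizon is not in the plan.** This stands, and it is an assumption here. If long-term means 5 years, the fitted value is stable once there is a failure (0.95 for one in 20). No prediction is then needed, and the observed proportion does the job.
- **Failure dates are recorded in weeks.** This helps, but the simulations already assume exact dates.

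A reader might infer that the long-term part of the aim cannot be met, or that the aim must be reworded. The documents do not support that: clinical and radiographic assessments are scheduled at 5 years, most of those outcomes have a planned test, and the 5-year visit can itself be the long-term result. A reader might also infer that the trial will report a false ranking of materials. Identical materials can indeed give widely different predictions, but the plan specifies no ranking and no test of the Weibull predictions.

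**Conclusion.** The concern holds in a limited form. Followed as written, the survival sentence can yield no estimate for an arm, or one that depends on the date of a single failure, and the plan has no rule for either case. The chance of at least one arm without a fit is 74%, 32% or 3% at assumed 5-year failure of 5%, 10% or 20%, with equal rates and no loss to follow-up. Predictions beyond 5 years are too imprecise to report as a rate per material across the failure rates and shapes simulated, though how imprecise depends on the shape: at 20% failure the lower end is 0.00 with shape 1.5 and 0.12 with shape 1.0. The failure rate, shape and 10-year horizon are all assumptions. The observed 5-year data, and the other long-term outcomes, are not affected. The change should be made, but this does not undermine the trial as a whole.

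**What to change.** - Make observed 5-year survival per arm the main survival result, by Kaplan-Meier with an interval that remains valid when no tooth fails: exact Clopper-Pearson if all teeth are followed. The usual Greenwood interval has zero width in that case and will not do.
- Keep any Weibull extrapolation as exploratory only. State its horizon, show intervals, fit all 60 teeth with a common shape and an arm-specific scale, and give no Weibull prediction for an arm with no failures.
- State that long-term means the 5-year visit. The aim then needs no rewording.

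This costs a few sentences and no extra teeth or visits. The trial gives up a headline prediction beyond 5 years, and the common shape is an assumption that so few failures can hardly test.
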